### **Outcome Measurements:**

Outcome measures include both clinical assessments and subjective outcome measures reported by the subject on different rating scales.

Distribution of the scores and the clinical evaluations will be examined and cut-points may be assigned to create categorical data. Statistical analysis of parametric data will be done using ANOVA techniques with corrections for repeated measures (when necessary); non-parametric data will be analyzed with Chi-squared techniques. Statistical significance will be defined as  $p < 0.05$ . Power is expected to be 0.8. Data stratification will be done where appropriate. Stratification variables include: pre-operative pain modality.

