### **Assessments:**

Post-operatively patients will be evaluated 1 and 2 hr post-operatively by the PACU nurse and 6 hrs post-operatively by a medical student or research coordinator. This person will not be aware of the patient's mode of analgesia. The medical student or research coordinator will evaluate at, 24, 48, and 72 hours post injection +/- 5 hours. If sent home they will be contacted via preferred contact method at, 24, 48, and 72 hours post-operatively. Patients will be asked to rate their pain on scale of 0-10. The amount of opioids used by the patient will be recorded as will any other adjuvant pain medication used. Any modality related complications will be recorded. The patients will be asked at 72 hours post-injection to fill out a quality of recovery and OBAS survey. All complications will be recorded from time of consent to last follow up date. Patients will be called at 3, 6, and 12 months post operatively to fill out a chronic pain survey.

All data will be recorded in a locked encrypted database. Data collection will continue until Postoperative day ( POD ) #3. Should patients be re-admitted to the hospital in the next two weeks (Up to POD #19) for pain a notation will be made in study records. Additional contacts by the research assistant or medical student will continue up until the 3, 6, and 12 month postoperative times.

An analysis of the total cost of analgesics (including patient costs for opioid prescriptions) will be tabulated at the conclusion of the study to determine the most cost effective treatment option as this will be added into the cost of hospitalization including the number of days each patient spent in the hospital.

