  - Amount of opioids left over after 3 days
  - Presence of nausea/vomiting in 3 days post operatively
  - Occurrence of any subsequent re-admission over the ensuing 1 month and any complications

The collected data will be compared between groups on a regular basis in order to evaluate the safety and efficacy of the study. All data will be stored in secure locations in the Research Office. Research coordinators working with physicians to collect data at appropriate intervals will ensure complete follow-up. Research coordinators will periodically check physician schedules to ensure that patients being seen for follow-up complete all required questionnaires. Monthly meetings will also be conducted to ensure all patients needing to be evaluated are seen at the appropriate time intervals and that all data is being entered into the appropriate database.

**Data Safety Monitoring:** Authorized study staff and investigators who have gone through HIPAA, CITI, and other data security training through the University of Minnesota will be collecting, managing, and analyzing data. All serious adverse events will be brought forward to the Anesthesia Data Safety Monitoring Board that is comprised of various senior staff anesthesiologists. A formal determination concerning the severity of the risk and the recommended actions required will be submitted in writing to the principle investigator. This report will be submitted to the Institutional Review Board along with the required UPIRTSO documents.

**Statistical Considerations:** The primary outcome measurement used in this study is total opioid use

A sample size of 112 (56 per group) will be enrolled in order to power our study at 80% to detect a 35% decrease in total post-operative opioid usage for our treatment group versus the control with an  $\alpha=0.05$ . This sample size was estimated based on previous estimates for postoperative analgesic consumption from similar trials reported in the Tam (2015) meta-analysis paper.

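### No test is named for the primary opioid total, data classed as non-parametric go to chi-squared, and cut-points need not be fixed before data are seen by arm

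*Combined protocol and SAP*

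**What the plan says.** The Statistical Considerations paragraph states that "The primary outcome measurement used in this study is total opioid use". It sizes the trial at 112 patients (56 per group) for 80% power at alpha 0.05 to "detect a 35% decrease in total post-operative opioid usage for our treatment group versus the control". It names no test and gives no mean or SD.

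The tests appear only under Outcome Measurements, in three statements:

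- On categorising outcomes, the section says "Distribution of the scores and the clinical evaluations will be examined and cut-points may be assigned to create categorical data".
- For the first class of outcome it specifies "Statistical analysis of parametric data will be done using ANOVA techniques", adjusted where measurements repeat.
- For the second class it specifies "non-parametric data will be analyzed with Chi-squared techniques".

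The section then sets significance at p < 0.05 and adds "Power is expected to be 0.8". It does not say how parametric data are told apart from the rest, which class the opioid total falls in, or when and by whom cut-points are set.

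Two other places bear on who may know the group results. The Assessments section says of the person collecting later outcomes that "This person will not be aware of the patient's mode of analgesia", and Blinding Procedure says the same of the research coordinator. The Data collection paragraph says "The collected data will be compared between groups on a regular basis in order to evaluate the safety and efficacy of the study".

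**The concern.** Chi-squared is a test for counts in categories. If a skewed amount or an ordinal score is judged non-parametric, the only route the plan lists is to cut it into categories and test those. No rank test is offered, although that is the usual method for such data. Pain and recovery scores clearly fall within this rule.

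The opioid total could fall within it too. Opioid is given on need both during and after surgery (Treatment technique), so skew or a share of patients with no use is plausible, although the documents give no distribution.

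Two things are at stake. Cutting an amount or score usually discards information and so power. And if the cut, or the choice between a cut and an uncut test, follows a look at the results by group, the stated 5% error rate no longer holds. The blinding described covers outcome assessors. The plan is silent on whether whoever chooses the analysis is blinded, and it provides for regular comparisons between groups.

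**Working it through.** **Inputs from the plan:** 56 per group, alpha 0.05 (taken as two-sided), power 0.80, a 35% decrease. **Assumed, because the plan gives none:** the distribution, the coefficient of variation (CV), the share of patients with no opioid use, and the number of cuts tried.

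**1. The plan's own figure.** For a two-sided comparison of means by normal approximation, n = 56 implies CV = 0.35 / [(1.960 + 0.842) × √(2/56)] = 0.35 / 0.529 = 0.661. With the t-test, the standardised effect giving 80% power is d = 0.534, so CV = 0.35 / 0.534 = 0.655. Without a mean or SD, the 112 can be neither confirmed nor refuted. It fits a comparison of means if the CV is about 0.66.

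**2. Cutting at the pooled median, normal data, same effect.** The proportions above the cut are Φ(±0.534/2) = 0.605 and 0.395, a difference of 0.2106 before rounding.

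- Formula power at 56 per arm: Φ[(0.2106 − 1.960 × √(0.5/56)) / √(2 × 0.605 × 0.395/56)] = Φ[(0.2106 − 0.1852)/0.0924] = 0.608.
- The real test is discrete. With 56 of 112 patients above the cut, it rejects only when one arm has 34 or more above it, which has an exact size of 3.72%. Simulated power is 0.57 as the test would be run, and 0.60 if adjusted to an exact 5% size.
- Formula n for 80% power: [1.960 × √0.5 + 0.842 × √(2 × 0.605 × 0.395)]² / 0.2106² = 87.3, so 88 per arm against 56.

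**3. Power by simulation** (20,000 trials per row, 56 per arm, two-sided 0.05, chi-squared without continuity correction):

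| Assumed data | t-test | Wilcoxon | Pooled-median chi-squared |
|---|---|---|---|
| Normal, d = 0.534 | 0.80 | 0.78 | 0.57 |
| Log-normal, mean 35% lower, CV 0.655 | 0.93 | 0.96 | 0.83 |
| Log-normal, mean 35% lower, CV 1.0 | 0.64 | 0.755 | 0.54 |
| No use in 30% v 54.5%, same amount among users | 0.41 | 0.65 | 0.58 |
| No use in 30% of both arms, amount 35% lower among users | 0.59 | 0.43 | 0.37 |

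Log-normal CVs of 0.8 and 1.2 give the same ordering as 1.0. The median split is below Wilcoxon in every row. It is below the t-test in every row except the fourth, where a test of any versus no opioid reaches 0.75.

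**4. Type I error, same set-up, no true difference:**

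- Uncut t-test: 4.2–4.9% for log-normal data with CV 0.655 to 1.2; 4.8% and 4.6% with 30% and 50% of patients at zero.
- One cut fixed in advance: 3.7% exact at the median; 4.7–4.9% at a quartile.
- Best of three quartile cuts by group result: 11–12%.
- Best of nine decile cuts by group result: about 24% (13% with continuity correction).
- Best of the t-test and three quartile cuts: 12–13%.

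**The case against.** The strongest reply is that the plan has a workable default. The trial is sized on a percentage decrease in an amount, from earlier estimates of analgesic consumption. That points to a comparison of means, and for two arms the ANOVA on offer is equivalent to a t-test. This stands: a reader can infer the intended primary analysis, and it would be too strong to say that nobody can tell what the stated power refers to. The plan does not say it, though, and it gives no rule that keeps the opioid total out of the non-parametric class.

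Second, the cut-point sentence speaks of scores and clinical evaluations and does not name opioid use. This also stands. A reader might infer that the primary outcome will be dichotomised. The documents do not say so; they only fail to exclude it.

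Third, a reader might infer that cuts will be picked by group result and that the trial therefore runs at an 11% or 24% error rate. The text supports neither step. Those figures describe a hypothetical search that the wording leaves open, and a single cut set blind to arm stays at or below about 5%. The regular between-group comparison is mainly an interim-look question. It matters here only because group results could be known when the analysis is chosen.

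Fourth, cutting is not always worse: any versus no opioid is the strongest test when the effect is on the share using opioid. That argues for fixing such a cut in advance rather than for forbidding cuts.

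**Conclusion.** The point holds as a gap and a poor rule in the wording, and it should be fixed. No test is assigned to the primary outcome, chi-squared is the only route listed for data called non-parametric, and cut-points may follow inspection of the data with no requirement to fix them before results are seen by arm. For skewed scores the rule is inferior as stated; for the opioid total the exposure is by inference.

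The loss from a median split against Wilcoxon is about 0.2 in power in the two main cases (0.78 − 0.57 = 0.21 for normal data; 0.755 − 0.54 = 0.215 for log-normal CV 1.0). Error inflation to 11% or 24% is what the text permits, not what it plans. All these sizes rest on assumed distributions and numbers of cuts, so confidence in them is moderate; the textual gap does not depend on them.

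A reader might also infer that ANOVA is unsuitable for skewed opioid data, or that chi-squared is wrong altogether. Neither follows. The t-test held its error rate in every null case run, and chi-squared is right for binary outcomes.

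**What to change.** In Outcome Measurements:

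1. Name ANOVA or the t-test on the uncut opioid total as the single primary test, with the difference or ratio of means and its 95% CI as the estimate. If Wilcoxon is preferred, report an estimate that matches it, such as the Hodges-Lehmann shift or the probability index. A ratio-of-means interval does not match Wilcoxon: the two disagreed on significance in 20–28% of simulated trials in three of the assumed effect scenarios (delta-method interval, itself an assumed choice).
2. Replace chi-squared with rank-based methods for non-normal continuous or ordinal scores such as pain and recovery. Keep chi-squared or Fisher for binary outcomes such as conversion to general anesthetic.
3. Require every cut-point, for example any versus no opioid, to be written down before data are seen by arm and used only in secondary analyses.

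The cost is wording, with no extra patients or visits. The investigators lose the freedom to choose the test or cut later. No test is best everywhere: the t-test gives up power to Wilcoxon under log-normal skew (0.64 against 0.755 at CV 1.0) and to any versus none if the effect is on the share using opioid (0.41 against 0.75). Wilcoxon gives up power to the t-test if the effect is only on the amount among users (0.43 against 0.59).

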**Benefits:**

There are no benefits to you from your taking part in this research. We cannot promise any benefits to others from your taking part in this research. However, possible benefits to others include pain relief and possibly shorter hospital stay with decreased risk of complications. The only alternative post-operative pain treatment options include intravenous or oral opioids. During the study period, any subject who prefers not to be involved in this study will be treated appropriately as determined by the surgeon and anesthesiologist. There will be no alteration in the post-operative program for those that decline enrollment in this study.

No parties will receive any specific direct benefits from this study with the exception of the patient. The physician and medical community at large may indirectly benefit from learning more about the post-operative pain options for these patients.

**Precautions and corrective actions:** All treatment arms will have the same post-operative protocol. All complications will be noted by the operating physician and reported to the IRB and research staff. Appropriate records will be made in the patient chart and the patient will be treated as needed by the operating physician.

**Project Medications:** All medications will be provided by the hospital pharmacy, and will be noted in the medicine administration record in the chart. No experimental medications will be evaluated in this study.

**Specimens to be collected:** None

**Data collection:** The surgeon, anesthesiology staff, and research staff will collect data. The data will be comprised of outpatient notes, inpatient records, operative reports, intra-operative photos and assessments, questionnaires, study follow-up evaluations. In addition to the surveys used to measure subjective and objective outcome, other data will be collected during patient interviews including:

- Demographic data
- Age
- Weight
- ASA class
- Type and duration of surgery
- VAS Score at 1, and 6, 24, , 48, , and 72 hours after surgery
- Length of stay in recovery room
- Amount of opioids given preop,intraoperatively and post-operatively
- Rate of conversion to general anesthetic
- Satisfaction with treatment
- Quality of recovery survey on 72 hours post-injection
- OBAS at 72 hours
- Chronic pain (pain disability index) at 3, 6, 12 months
- At 72 hours the following will be recorded:
  - Any persistent need for analgesics
  - Total length of stay
  - Total Use of opioids per day

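### No covariate is pre-specified for the opioid comparison, although prognostic candidates are already collected; a small baseline set fixed in advance may gain precision at little cost

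*Combined protocol and SAP*

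**What the plan says.** The Statistical Considerations section states: "The primary outcome measurement used in this study is total opioid use". It enrols 112 patients, 56 per group, "in order to power our study at 80% to detect a 35% decrease in total post-operative opioid usage" at an alpha of 0.05. The Outcome Measurements section repeats "Power is expected to be 0.8" and gives the method: "Statistical analysis of parametric data will be done using ANOVA techniques with corrections for repeated measures (when necessary". Data judged non-parametric go to Chi-squared, and cut-points may be set after the distributions are examined. Stratified analysis is left optional. The one variable named for it is the pre-operative pain modality, which is not defined. No covariate and no regression model are named.

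The data-collection list includes age, weight, ASA class and "Type and duration of surgery", with no stated role in the analysis. The randomization procedure is a random number drawn per patient in the pre-op area, with no stratification or blocking described. The treatment-technique text assigns patients having lumpectomy with axillary dissection to general anesthetic from the outset.

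**The concern.** Age, weight, ASA class and the planned procedure are all fixed before allocation. If they predict opioid use, two things follow from leaving them out of the model. The variation they explain stays in the error term, and any chance difference between arms in these variables stays in the estimated treatment effect. The design does nothing to balance them. Planned procedure stands out because the protocol itself ties axillary dissection to a different anesthetic.

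The trial is sized at 80% power, and the sample-size text states no allowance for losses, while the enrollment section removes incomplete patients from the analysis. Precision available from data already held is therefore worth considering.

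Timing also matters. The data-collection text provides for regular comparisons between groups during the trial, and stratification is left to later judgement. A covariate set chosen after such comparisons would be open to the charge of selection; one fixed now would not.

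**Working it through.** **Inputs from the documents:** 56 per group, power 0.80, alpha 0.05, 35% decrease.

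**Assumptions:** a two-sided test (sidedness is not stated), and R-squared of the baseline set with opioid use from 0 to 0.20 (not in the documents).

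**Step 1: the plan's own figure.** No mean or SD is given, so 112 cannot be reproduced directly. Solving backwards with the noncentral t (110 df, critical value 1.982), 80% power with 56 per group requires d = 0.534:

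- noncentrality = d × √(56/2) = 0.534 × 5.292 = 2.826, which gives power 80.0%
- implied coefficient of variation = 0.35 / 0.534 = 0.655

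The normal approximation gives d = 0.529 and a coefficient of variation of 0.661.

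**Step 2: effect of adjustment.** With k covariate degrees of freedom, the residual variance falls by the factor (1 − R²). The variance of the treatment difference rises by about 1 + k/(109 − k), because chance covariate imbalance has to be estimated. The error df fall to 110 − k:

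noncentrality = 2.826 / √[(1 − R²) × (1 + k/(109 − k))]

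- k = 3: inflation 1 + 3/106 = 1.0283, 107 df
- k = 4: inflation 1 + 4/105 = 1.0381, 106 df

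| R² | noncentrality, k = 3 | power, k = 3 | noncentrality, k = 4 | power, k = 4 |
|---|---|---|---|---|
| 0 | 2.787 | 78.9% | 2.774 | 78.5% |
| 0.05 | 2.860 | 80.9% | 2.846 | 80.5% |
| 0.10 | 2.938 | 82.9% | 2.924 | 82.6% |
| 0.20 | 3.116 | 87.0% | 3.101 | 86.7% |

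Break-even with the unadjusted 80% is R² of about 0.03 for k = 3 and about 0.04 for k = 4. Age, weight, a two-level ASA class and planned procedure make k = 4.

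Using the factor 1/(1 − R²) alone gives 82.0%, 84.0% and 88.0% at R² 0.05, 0.10 and 0.20, and no loss at 0. Those figures omit the cost of estimating the covariates and are too favourable.

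**Step 3: chance imbalance.** With 56 per arm, a standardised covariate difference has standard error √(2/56) = 0.189. The chance that a given continuous covariate differs by more than 0.2 SD is the two-sided normal tail beyond 0.2/0.189 = 1.058, or about 29%. For at least one of three independent covariates it is 1 − 0.71³, or about 64%.

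**The case against.** The strongest reply is that nothing here is an error. Under randomisation an unadjusted comparison is valid, and chance imbalance is already allowed for in its standard error. That stands: a reader might infer that the planned analysis is biased, and the documents do not support that.

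A reader might also infer that precision is certainly being lost and could be recovered for nothing. Neither part is supported. No passage links age, weight or ASA class to opioid use, so R-squared is unknown. Below about 0.03 to 0.04, adjustment loses a little power.

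The wording is also more open than a fixed unadjusted ANOVA: it allows cut-points, Chi-squared and optional stratification. What can be said is that no covariate set or model is pre-specified. For the same reason, one cannot say that the plan will stratify on duration of surgery or on conversion to general anesthetic. Neither is named for that use; the text merely does not exclude them.

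Finally, an implied coefficient of variation near 0.66 makes skewed opioid totals plausible, so a raw-scale linear model needs a stated way of handling skew. Adjustment also does not repair the removal of incomplete patients after randomisation. Both points stand and limit what this change can do; neither removes the case for it.

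**Conclusion.** The point holds as a missed efficiency in a valid analysis. If the baseline set explains 5% to 10% of opioid variance, the net gain is about 1 to 3 points of power with three covariate df, and about 0.5 to 2.6 points with four. At 20% it is about 7 points. If the set explains nothing, the loss is about 1 to 1.5 points. These figures rest on an assumed R-squared, a two-sided test, an effect size back-solved from the stated sample size, and all 112 patients analysed. The balance favours adjustment because the possible loss is small and bounded. Fixing the covariates now also removes a later choice, whatever R-squared proves to be.

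**What to change.** In Outcome Measurements, state that:

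- total opioid use is compared by a linear model with arm plus age (continuous), weight (continuous), ASA class (in a grouping fixed beforehand) and planned procedure (with or without axillary dissection); repeated pain scores use the mixed-model equivalent with the same covariates;
- the set is fixed before any data are seen by arm;
- if opioid totals are skewed, a transformation named in advance or robust standard errors will be used, with the rule for choosing written down now;
- the adjusted difference with its 95% confidence interval is the primary result and the unadjusted difference is supportive;
- duration of surgery and conversion to general anesthetic are neither covariates nor strata, because both arise after allocation and conversion is itself a secondary outcome.

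The cost is a few sentences, no extra visits or patients, and at most about 1 to 1.5 points of power if the covariates are not prognostic. No new variable is needed. However, the data-collection list does not say whether type of surgery means planned or performed, so the planned procedure should be the one recorded, before allocation.

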### **Secondary Objectives:**

1. To determine if a pectoralis 1 and 2 block with liposomal bupivacaine provides decreased maximal pain scores when compared to incisional bupivacaine infiltration
2. To determine if a pectoralis 1 and 2 block with liposomal bupivacaine provides decreased rate of conversion to general anesthetic when compared to incisional bupivacaine infiltration
3. To determine if a pectoralis 1 and 2 block with liposomal bupivacaine improves quality of recovery score post-operatively when compared to incisional bupivacaine infiltration.
4. To observe the effect on chronic postoperative pain in patients who have breast surgery.

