(scores will be evaluated at 1 hr, 2 hr, 6hrs, 24hrs, 48hrs, 72hrs). They will record daily opioid use, any modality related complications, how many phone calls were made regarding pain control and modality related complications. At time period 72 hours a Quality of recovery survey (see appendix) and OBAS (see appendix) survey will be presented to patient. Patients will be offered phone calls for contact, but patients may opt to be contacted via text message if they do not wish to have phones calls. We will provide patients with an additional consent for text messaging if they wish to use this method.

At 3 months, 6 months, and 12 months patients will be called to answer a survey with regards to chronic pain.

Patients will be instructed to take acetaminophen 1000 mg every 8 hours while at home for 3 days. They will be given a prescription of opioid pain medications either oxycodone or hydromorphone and will be instructed to take as needed for pain.

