### **Enrollment procedures:**

Patients will be recruited from the group of adult surgical patients at the University of Minnesota undergoing partial mastectomy procedures. Patients will be approached in either the surgeon's clinic or pre-assessment clinic by a research staff member to determine their interest in participation. Subjects interested in the study will be presented with consent and Health and Insurance Portability and Accountability Act (HIPAA) forms, with the REDCap e-consent process being preferentially used. The patient will review the forms with the surgeon, anesthesiologist or other study staff. Subjects will be reminded that participation is completely voluntary, and that they may stop participation at any time without question or penalty. The surgeon or anesthesiologist will answer any questions that the subjects may have about the study. If the patient decides to participate, they will be asked to sign the consent and HIPAA forms. One copy will be saved for study records, and the subject will be provided with a copy of the forms for their own records. If they need additional time to consider enrollment, they will be asked if we can reach out to them by phone the night before surgery or if we should revisit the study with them on the day of surgery. If the patient is unable to be consented prior to day of surgery, the research staff will approach them in the preoperative surgical area. These patients will have significant time to review the study with research staff as well as the physicians performing the procedure due to the fact they arrive several hours prior to their scheduled surgery. All subjects will have enough time to ask questions about the study and the potential risks involved regardless of which venue they are consented. Any patient that refuses to participate in the study at any time point will be placed on a secured list to avoid duplicate attempts to recruit them. All forms will be locked and stored in a file cabinet in the research department. Enrolling consecutive patients will help reduce selection bias. Any patient who does not complete all necessary paperwork and answer questions at the appropriate time intervals will be eliminated from the study. Patients lost to follow-up, or patients who decide not to participate in the study after initial enrollment, or patients who are eliminated from the study for any reason will have their study records shredded and will not be included in the final data-analysis.

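### The rule eliminating patients who miss a question interval, combined with an ANOVA that in its classical form needs complete rows, leaves the pain comparison to complete responders only and also shrinks the primary opioid analysis.

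*Combined protocol and SAP*

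**What the plan says.** Four parts of the combined protocol and SAP bear on this point.

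- **Elimination rule.** Enrollment procedures states: "Any patient who does not complete all necessary paperwork and answer questions at the appropriate time intervals will be eliminated from the study". Those lost to follow-up, those who change their minds after enrolling, and those eliminated for any reason "will have their study records shredded and will not be included in the final data-analysis". The rule is not limited to any one endpoint.
- **Analysis method.** Outcome Measurements assigns parametric data to "ANOVA techniques with corrections for repeated measures (when necessary" and non-parametric data to chi-squared techniques. It does not name pain, give a model form or say how missing values are handled. No other section gives a missing-data method.
- **Pain schedule.** Treatment technique says "scores will be evaluated at 1 hr, 2 hr, 6hrs, 24hrs, 48hrs, 72hrs", and the Assessments section agrees. The Data collection list has "VAS Score at 1, and 6, 24, , 48, , and 72 hours after surgery", without the 2-hour score. Under Assessments, the PACU nurse takes the 1- and 2-hour scores and a student or coordinator takes the 6-hour score. Patients already at home are contacted remotely at 24, 48 and 72 hours.
- **Endpoints and size.** The pain objective is secondary: whether the block "provides decreased maximal pain scores when compared to incisional bupivacaine infiltration". Statistical Considerations says "The primary outcome measurement used in this study is total opioid use" and "A sample size of 112 (56 per group) will be enrolled". It states no allowance for loss.

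**The concern.** A patient who gives five pain scores and misses the sixth has supplied most of the information wanted. Under the elimination rule that patient contributes nothing to pain, opioid use or any other outcome. If the rule were lifted and nothing else changed, a classical repeated-measures ANOVA would set the same patient aside again in the pain analysis, because it needs a full row of scores.

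Two things are at stake. The first is precision: small miss rates at each contact add up to a sizeable loss of whole patients, and the sample size has no margin for it. The second is bias. Patients who do not answer may be those in more pain, more sedated or recovering differently. They also know which treatment they had, since one arm receives a preoperative ultrasound-guided block and the other goes straight to the operating room. A comparison restricted to those who answered every time is no longer a comparison of the randomized groups. The documents hold no data on whether such bias would occur or in which direction, so it is a risk and not a demonstrated effect.

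**Working it through.** **Inputs from the documents.** 56 per arm; 80% power; alpha 0.05 (taken as two-sided, which is not stated); a 35% decrease in opioid use; six pain times in Treatment technique and Assessments, five in Data collection; three explicitly remote contacts in Assessments.

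**Assumed, because the documents give no figure.** A miss rate m per contact, independent between contacts; 5% as the worked case, with 2% and 10% as a range.

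**Step 1: the plan's own figure.** The stated 112 cannot be reproduced, because neither a control mean nor an SD is given. Solving backwards with the normal approximation:

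d = (1.960 + 0.842) × √(2/56) = 0.529

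This implies SD / control mean = 0.35 / 0.529 = 0.66. The sample size is consistent with that ratio, but the documents do not confirm it.

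**Step 2: patients lost.** The share complete over K contacts is (1 − m)^K.

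- K = 3, m = 0.05: 0.95³ = 0.857, so 14.3% lost, leaving 56 × 0.857 = 48.0 per arm.
- K = 6, m = 0.05: 0.95⁶ = 0.735, so 26.5% lost, leaving 56 × 0.735 = 41.2 per arm.

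With K = 6, the share of scores actually obtained and then discarded is 1 − 0.735/0.95 = 22.6%.

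**Step 3: power.** Power = Φ(d√(n/2) − 1.96), with d = 0.529.

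- n = 48.0: Φ(2.594 − 1.960) = 0.74.
- n = 41.2: Φ(2.402 − 1.960) = 0.67.

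| m per contact | Contacts that can be missed | Lost | Left per arm | Power |
|---|---|---|---|---|
| 2% | 3 | 5.9% | 52.7 | 78% |
| 2% | 6 | 11.4% | 49.6 | 75% |
| 5% | 3 | 14.3% | 48.0 | 74% |
| 5% | 5 (Data collection list) | 22.6% | 43.3 | 69% |
| 5% | 6 | 26.5% | 41.2 | 67% |
| 10% | 3 | 27.1% | 40.8 | 67% |
| 10% | 6 | 46.9% | 29.8 | 53% |

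The d here is the one implied by the opioid sample size. The power column therefore bears on the primary comparison, within the limits of Step 1. For pain it shows only what the same loss would do to any comparison that started at 80%.

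**Step 4: what each change recovers.** Take the average pain difference over six contacts, m = 5%, and a constant correlation ρ between scores. A patient with k scores carries information k / (1 + (k − 1)ρ). Averaging this over the binomial distribution of k, dividing by the value at k = 6 and multiplying by 56 gives the effective number per arm under a mixed model: 55.1 at ρ = 0.3 and 55.8 at ρ = 0.7.

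- Elimination rule kept, either model: 41.2 per arm.
- Elimination rule lifted, classical repeated-measures ANOVA: 41.2 per arm for pain.
- Elimination rule lifted, mixed model: 55.1 to 55.8 per arm for pain.

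Neither change alone recovers anything for the repeated pain analysis. Lifting the rule does by itself restore patients to the primary analysis wherever their opioid use was recorded.

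**The case against.** The strongest objection concerns cause. The elimination rule acts before any model is fitted, so ANOVA as planned would meet no incomplete rows. A reader might infer that ANOVA is what discards the data and that substituting a mixed model would restore it. The documents do not support that: while the rule stands, both models receive the same patients. This part of the objection stands, which is why the elimination rule comes first here. It does not remove the analysis half of the point, because Step 4 shows that repairing the rule alone leaves the repeated pain analysis where it was.

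A second objection is that Outcome Measurements does not commit to a classical repeated-measures ANOVA of six pain scores. It says corrections are made when necessary, it allows cut-points, and the objective is maximal pain, which could be one value per patient. This also stands in part: the text is open. But it is the only method offered for repeated continuous data, and pain is the most closely repeated outcome.

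Third, the 26% loss applies one miss rate to scores taken by a nurse in recovery as well as to those obtained remotely. That is fair. Only three contacts are explicitly remote, and reading the 6-hour score as remote too is an inference. The 14% figure belongs beside the 26%. Misses by the same patient are also likely to cluster, which would reduce the number of patients lost.

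Finally, the bias argument has limits. Non-response that depends only on arm does not by itself bias the comparison. If it depends on pain that was never observed, a mixed model is biased too.

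**Conclusion.** The point holds in this form: followed as written, the plan gives a secondary pain comparison among complete responders only, and the elimination rule also reduces the primary opioid analysis. At an assumed 5% independent miss rate per contact, the loss is about 14% to 26% of patients, and 80% power becomes about 74% to 67%. The lower loss counts only the three explicitly remote contacts and the higher counts all six.

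These figures rest on an assumed miss rate, on independence, and on a d solved back from the opioid sample size. They count contacts up to 72 hours only; the documents do not say whether the rule extends to the 3-, 6- and 12-month surveys, and if it does the loss would be larger. A reader might take 67% as the power of the pain analysis. The documents do not support that, because no pain effect size or SD is stated. Bias is a plausible risk that the documents cannot quantify. The change should be made: it is inexpensive and affects the primary outcome as well as a secondary one.

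**What to change.** 1. **Enrollment procedures.** Replace the elimination, shredding and exclusion wording. Retain every randomized patient and all data already collected, and analyse them in the assigned arm, subject to any withdrawal of consent for use of data. This must come first.
2. **Outcome Measurements.** For repeated pain scores, specify a linear mixed model with arm, time and arm-by-time terms and an unstructured covariance, using all observed scores. For single summaries such as maximal pain, specify a two-group rank test. Say whether maximal pain is one value per patient or one per contact, and how it is formed when a contact is missed.
3. **Sensitivity analysis.** The mixed model relies on data being missing at random. Add one simple analysis that departs from this, for example assigning worse pain to missed contacts over a stated range, and report missed contacts by arm and time.
4. **Time points.** Reconcile the 2-hour score between Treatment technique and Assessments, which include it, and the Data collection list, which does not.

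The cost is a protocol amendment to the retention and record-handling text, a few sentences of analysis wording, and matching consent language if that repeats the rule. Standard software suffices, and no extra patients or visits are needed.
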